Protocol Template Guidance

For Submissions to CORIHS

TITLE: Aromatherapy for management of back pain in the Emergency Department

INVESTIGATORS: [name] MD / [name] MD / [name] BS
Department of Emergency Medicine

A. SPECIFIC AIMS

This study aims to research the use of aromatherapy for pain control in the emergency department, specifically, acute back pain. Aromatherapy, particularly Rose Essential Oil (Rosa damascena) has been studied in recent literature and shown to be effective versus placebos for the control of acute pain with lasting effects during burn dressing changes and post-operative pain management. These studies have been small and specific to discrete clinical conditions. Their evidence supports the use of aromatherapy for acute pain control with additional patient satisfaction benefit, but they are not yet externally validated to more common conditions facing emergency medicine physicians. We chose to study acute isolated back pain and sciatica presenting to the emergency department and the use of Rosa damascena essential oil versus a control of Almond Oil for the treatment of isolated back pain and sciatica. We will investigate the use of aromatherapy in pain management by measuring and comparing pre- and post-treatment pain levels using a 100 mm visual analog scale (VAS) for pain. A significant reduction in pain by 13 mm on the VAS has been previously demonstrated as the minimal clinically important difference for treatment of pain (). Our primary endpoint will be the evaluation of significant change in VAS score greater than 13 mm between both groups immediately following a 30 minute blinded aromatherapy treatment and again 30 minutes later. Our secondary measures include patient satisfaction, need to rescue medication (its type and dose), and subjective changes in pain.

B. Background and Significance

Aromatherapy has been hypothesized to be an effective management strategy for acute pain control. Its use has been recently demonstrated in Iran, using Rosa damascene (Damask Rose) essential oil. Rosa damascene is believed to possess anti-anxiolytic, sedative, anticonvulsive, and analgesic effect on the CNS when delivered through the olfactory system (Mohebitabar et al. 2016). This theory is believed to be in part due to the lateral gate theory of pain control and a stimulant's ability to inhibit transmission of stimuli through pain fibers. However, while any olfactory stimulant might be hypothesized to do just that, only Rosa damascena has been shown to produce significant reduction in pain on the VAS as well as patient satisfaction when compared to scented placebos like Almond Oil. Rosa damascene has been shown to improve pain control during dressing changes of second- and third-degree burns (Bikmoradi et al 2016). It has also been shown effective and equal to NSAID treatment of immediate post-operative pain in children (Marofi et al. 2015). It may be an affordable and easy-to-use modality for pain control in the emergency department. Its prior studies are small in sample size and carry little external validity that could be applied to an American Emergency Department population. We aim to assess whether aromatherapy using Rosa Damascena is reproducible in the emergency department for control of isolated and acute back pain, two common painful conditions seen with poor evidence for proper pain control. Validity of Rosa damascene aromatherapy in acute back pain and sciatica may open new doors of pain control to be researched in the emergency department and will further characterize the use of aromatherapy in modern medicine.

C. Preliminary Studies

The known external studies of Rosa damascene have been cited above and will be presented in the references section. We have not yet studied aromatherapy in the emergency department and will be completing this study fresh, based on methodology used in external aromatherapy and back pain treatment studies. Our MCID of 13 mm on the VAS has been studied repeatedly and validated as the minimal VAS change needed for a patient to express significantly subjective improvements in pain (Gallagher, Leibman, and Bijur 2001)(Jensen and Chen 2003). Successful pain treatment has been shown by using 3-5 drops of 40% Rosa damascene oil on a cotton ball or gauze pad 20-30 cm from a patients face for 30 minutes (Bikmoradi et al. 2016). Additionally, uses of rescue medications and patient satisfaction have been commonly used as secondary measures in both aromatherapy and

landmark back pain treatment studies. Patient demographics include age, gender, comorbidities, prior treatment, BMI, education, marital status, and pain identifiers have been repeatedly used to assess patient demographic distribution in many benchmark Emergency Medicine acute pain management studies (Chang et al 2015.)(Friedman et al. 2015).

D. Research Design and Methods

Rationale and Overview

Isolated acute back pain (less than 2 weeks duration) and sciatica are common complaints to the emergency department requiring acute pain management with often chronic follow-up. Their abundance in the ED as well as poorly defined treatment recommendations make them an excellent candidate to study the use of aromatherapy in the emergency department. We will replicate the Rosa damascena trials referenced above in similar protocols, patients will be recruited if they fit the attached inclusion criteria and do not meet exclusion criteria. Patients will be treated with either Almond Oil extract or Rosa damascena extract, and both the investigator and patient will be blinded to the control arm. A VAS pain scale will be recorded before treatment, after 30 minutes of treatment, and after a following 2nd 30 minutes. Patients will additionally be asked about their satisfaction and subjective changes in pain, they will be blinded to their prior VAS line placements for proper evaluation of objective pain level changes. Demographics thought to contribute to the sensation of pain, expression of pain, and response to pain treatment will additionally be collected without entangling PHI. Finally, the use of rescue medication such as NSAIDs or Narcotics at the treating physician's discretion will be recorded as an indicator of treatment failure and complication. Pain will be qualified in its type, locations, duration, immediate episodes prior to presentation, and prior remote episodes in the patient's lifetime health history. Pain will also be quantified by attempted at-home treatments prior to presentation.

Research Site

The entirety of this prospective clinical trial will be conducted at the Stony Brook Hospital Emergency Department, an ED with over 80,000 annual visits.

Study Sample

Patients will be recruited into this study by an investigator in the Stony Brook Emergency Department. A sample size was calculated to be 30 patients for each treatment arm based on a power of 0.80, desired p value below 0.05, and 95% confidence intervals with the anticipated possibility of patient loss or desire to withdraw during treatment. Patients will be approached for recruitment after an attending or resident physician has seen them and does not anticipate immediate need for narcotic pain medication, immediate imaging, or immediate threats to life or limb. Patients will be included by the attached inclusion and exclusion criteria. Double-blinding will be ensured by block randomization of each treatment arm, performed outside of the emergency department. In the Emergency Department Research Offices, the two treatment arms will be allocated into identical, individual vessels with only a codified label applied to each. Using block randomization, 30 treatments will be distributed to each arm in secret by a clinical research assistant or [name]. Each treatment will be codified individually and recorded in secrecy and kept from the investigators, [name] and [name]. Randomization will then arrange the total 60 treatments in longitudinal order for sequential random treatments to be selected as each patient is recruited.

Screening

Patients will be approached in private and the name, title, and role of the investigator explained after asking permission to speak with the patient. The patient will be told that we are conducting a clinical research trial for the treatment of acute back pain and sciatica. Aromatherapy will be explained as the treatment of interest and a modality that has been tested and proven in other types of pain. The use of Almond products and Rose products will be briefly discussed with the patients. Patient's will be asked about any allergies and then asked specifically about allergies to Almonds, Roses, perfume, and ibuprofen. Patient will be informed that speaking with the investigator is entirely optional, as is participating in the study, as there may be no direct benefit to them despite disclosure of their private information to the investigator. An Inclusion and Exclusion form will be reviewed with the patient and

their chart, noting their sequential patient number in this study as the only de-identified patient ID. No PMI will be collected; no MRN, address, phone number, emails, name, SSN, DOB, chief complaint, PMH, PSH, or medications will be recorded. The risks and benefits will be explained to the patient including risk of allergy, risk of no change in pain, benefit of pain improvement, and benefit of contribution to medical research. The consent form will be reviewed in full and any questions answered. Those patients interested in participating and able to grant consent will do so.

Procedures

Rosa damascena 40% and Almond Oil 40% kept outside of the ED will be prepared each day and dispersed into identical vessels with randomized identification numbers. The coded numbers and their respective modality will be recorded by an investigator not involved in delivery and kept secured. Patients will be chosen into random treatment arms by block randomization and their coded treatment recorded on the patient data sheet. Patients will be given 4 drops of either modality (40%) on a cotton ball kept between 20 and 30 cm from their face for 30 minutes.

With regards to study blinding, the treatments will be randomly assigned and the patients will not be told which treatment they are receiving. The patients will be aware that the study involves Rose and Almond scents and will likely be able to identify the scent used in their treatment. However, at the end of the study procedures, an independent observer will assess the patient's pain after the aromatherapy has been removed from the room, and will not be aware of which patients received which treatment.

E. Statistics

VAS differences immediately after treatment and 30-minutes following will be aggregated from their respective 100 mm VAS for pain and the change calculated for each patient. One-tailed paired t-Tests will be then conducted on the means after standard deviation is calculated and compared between treatment and control groups. A chi-squared test will then be applied between both groups for analysis of significant differences in patient satisfaction and subjective reports of pre- and post-treatment pain. The use of rescue medications by type and dosage will be measured as a percentage of each group and compared via t-Test between both groups.

F. Funding

Rosa damascene and Almond Oil are affordable and readily available over-the-counter. This trial requires no significant funding to be conducted.

G. HUMAN SUBJECTS RESEARCH PROTECTION FROM RISK

Risk to Subjects

This study poses minimal risks to its enrolled subjects. Subjects will not be exposed to systemic treatments. Their anticipated risks include failure to control pain, dislike of the randomized aromatherapy agent, and (rare) allergic reaction. The former will be reduced by screening for allergies to flowers, almonds, or perfumes.

Adequacy of Protection Against Risks

Patients are well-protected against the aforementioned risks. Rescue medications will be used at the treating physician's discretion for those patients without proper pain control as a result of the trial. Patients with allergies are anticipated to be extremely rare and will be screened out by questionnaire and inclusion/exclusion criteria. The study will be conducted entirely in the Emergency Department, where physicians and nurses trained in emergency medicine are available to treat any unforeseeable risk such as anaphylaxis.

Potential Benefits of Proposed Research to the Subjects and Others

Patients may benefit directly from this study through relief of their acute pain. The benefit to society will be that of the evaluation of aromatherapy as a pain management tool in the emergency department. This research will answer if it is an appropriate modality for the emergency department and whether its evidence elsewhere is applicable and warrants further study.

Importance of the Knowledge to be Gained

The knowledge gained in this trial may provide a groundwork for future use of aromatherapy treatment of acute pain in the emergency department. In the very least, it will demonstrate whether prior aromatherapy using Rosa damascena are externally valid and worth further research or not reproducible in the acute back pain patient.

H. Literature Cited

Bijur, Silver, and Gallagher. 2001. Reliability of the Visual Analog Scale for Measurement of Acute Pain. *Academic Emergency Medicine* 8(12): 1154-1157

Bikmoradi et al. 2016. The Effect of Inhalation Aromatherapy with Damask Rose (*Rosa damascene*) Essence on Pain Intensity after Dressing in Patients with Burns: A clinical Randomized Trial. *Iranian Journal of Nursing and Midwifery Research* 21(3):247-254

Chang et al. 2015. Comparative Analgesic Efficacy of Oxycodone/Acetaminophen Versus Hydrocodone/Acetaminophen for Short-Term Pain Management in Adults following ED Discharge. *Academic Emergency Medicine* 22(11):1254-1260

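### The primary endpoint has two time points and a 13 mm clause but no rule for success. Under stated assumptions, the literal reading has power below 0.5 at a true 13 mm, and the named paired t-test does not fit two separate arms.

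*Combined protocol and SAP*

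**What the plan says.** Section A (Specific Aims) defines a single primary endpoint as a "significant change in VAS score greater than 13 mm between both groups", assessed "immediately following a 30 minute blinded aromatherapy treatment and again 30 minutes later". It calls 13 mm the minimal clinically important difference. Section C (Preliminary Studies) describes the same figure at the level of one patient: "validated as the minimal VAS change needed for a patient to express significantly subjective improvements in pain".

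Section D (Rationale and Overview) schedules the readings without ranking them: "A VAS pain scale will be recorded before treatment, after 30 minutes of treatment, and after a following 2nd 30 minutes". Section D (Study Sample) gives 30 per arm from a "power of 0.80, desired p value below 0.05". It states no target difference, SD, sidedness, loss rate or time point.

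Section E (Statistics) says "VAS differences immediately after treatment and 30-minutes following will be aggregated" and a change calculated for each patient, and then "One-tailed paired t-Tests will be then conducted on the means", compared between treatment and control. It does not mention 13 mm, rank the time points or divide alpha.

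**The concern.** Two questions about the primary claim are open. Must the difference succeed at both times, or is one enough? Is 13 mm a condition on the observed difference, a margin to be tested against, a cut-off for each patient, or the difference the trial was planned to detect? The Aims sentence applies it between groups, while Section C defines it within a patient. The same data could therefore be called positive under one reading and negative under another, and the choice could be made after the results are known.

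Separately, each patient receives one oil, so the between-arm comparison has no pairs. Taken at face value, a paired test compares before with after within an arm, which is not a comparison of rose with almond oil.

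**Working it through.** **The plan's own figure.** The 30 per arm cannot be reproduced from stated inputs, because the difference, SD and loss rate are not given. With 13 mm assumed as the difference and SD 20 mm, one-sided 0.05 and power 0.80:

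n per arm = 2 × (1.645 + 0.842)² × 20² / 13² = 29.3, rounded up to 30.

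The t-test power at 30 per arm is 0.80. SD 20 is thus one value consistent with the plan, with no room for loss. It is not the only one: one-sided with SD 18 gives 24, and 24 / 0.80 = 30 after 20% loss; two-sided with SD 18 gives 31.

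**Assumptions.** Two-sample t-test on VAS change between arms, one-sided 0.05, 30 analysed per arm, and the same true difference at both times. The correlation r between the two changes is 0.5, 0.7 or 0.9. The main SD is 20 mm, with 25 and 30 mm as a range. The SDs and correlations are not in the documents.

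**Fixed quantities at SD 20.** SE of the difference = 20 × √(2/30) = 5.16 mm. Critical t on 58 df = 1.672. Smallest significant difference = 1.672 × 5.16 = 8.6 mm (10.8 mm at SD 25, 12.9 mm at SD 30).

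**Readings at SD 20**, by simulation; entries are for r = 0.5 / 0.7 / 0.9 and agree across runs to about 0.1 percentage point:

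| Reading | False claims (%) | Power at a true 13 mm |
|---|---|---|
| Both times, significant and observed >13 mm (literal) | 0.06 / 0.14 / 0.30 | 0.33 / 0.37 / 0.43 |
| Both times significant, no 13 mm condition | 1.2 / 1.9 / 3.2 | 0.69 / 0.71 / 0.75 |
| Either time, significant and observed >13 mm | 1.1 / 1.0 / 0.9 | 0.67 / 0.63 / 0.57 |
| Either time significant, no 13 mm condition | 8.9 / 8.0 / 6.9 | 0.91 / 0.89 / 0.85 |
| One named time, no 13 mm condition | 5.0 | 0.80 |

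**Why more patients do not rescue the literal reading.** If the true difference is 13 mm, the observed difference exceeds 13 mm half the time at one time point, by symmetry, at any n. At both times the large-sample probability is 1/4 + arcsin(r)/(2π) = 0.333, 0.373 and 0.428. Simulation at 500 per arm gives 0.334, 0.375 and 0.429. At 30 per arm and SD 20, power of 0.80 under this rule needs a true difference of 19.0, 18.7 or 18.2 mm.

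**Larger SDs.** The literal reading gives false claims of 0.39–1.3% (SD 25) and 1.0–2.6% (SD 30), with power 0.33–0.43 and 0.31–0.41. The either-time rate without the 13 mm condition does not depend on SD. With the condition, either-time false claims are 3.1–4.0% at SD 25 and 5.8–7.5% at SD 30. Single-time power falls to 0.64 and 0.51.

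**Readings outside the table.** A test of the null that the difference is at most 13 mm has power equal to its alpha at a true 13 mm: about 0.05 at one time, 0.07–0.09 at either and 0.01–0.03 at both. If 'aggregated' means averaging the two changes, there is one test, with 5.0% false claims and power 0.89 / 0.85 / 0.82 at SD 20. A comparison of the proportions improving by more than 13 mm is also possible.

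**The case against.** The strongest reply is that the Aims wording joins the two times with 'and' and carries the 13 mm clause, so it already implies a strict rule that cannot inflate the error rate. A reader might infer from the two untested-for-multiplicity time points that the trial runs at about 9% false claims. The documents do not support that. The figure requires changing 'and' to 'either' and also dropping 13 mm. This part of the reply stands, and it moves the main problem to power. It does not close the gap, because Statistics never confirms the strict rule and omits 13 mm altogether.

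A reader might also infer that 13 mm has no role in the plan, or that 0.33 to 0.91 spans every possible power. Neither holds. The figure is labelled as the minimal clinically important difference and sits in the endpoint; only its part in the decision is missing. The margin, responder and averaged readings lie outside the table, and the margin test falls far below 0.33.

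Finally, SD 20 is back-solved from one-sided testing with no loss, although Study Sample says loss was anticipated. That is fair, so the sizes are illustrative. The power limit of the literal rule at a true 13 mm does not depend on SD.

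**Conclusion.** The point holds and should be fixed. One primary endpoint sits at two times with a 13 mm clause, no rule says what makes the trial positive, and the named paired test does not match a comparison of independent arms.

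On the plan's own words the main cost is power: 0.33–0.43 at a true 13 mm (SD 20, correlation 0.5–0.9), and below 0.5 at any sample size if the true difference is 13 mm at both times. Inflation arises only if either time is allowed to suffice: about 7–9% without the 13 mm condition, or 5.8–7.5% with it if the SD is as large as 30 mm. The documents do not establish an error rate above 5%; they leave the rule open. All sizes rest on the assumed test, SD, correlation, equal effects at both times and 30 analysed per arm. The absence of a success rule and the mismatch of the paired test rest on the text alone.

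**What to change.** Make these changes before unblinding.

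1. In Statistics, replace the paired test with an independent two-sample t-test of VAS change from baseline between arms, and remove or define 'aggregated'.
2. Name one primary time point, chosen by the sponsor, and test the other at the same level only if the first is significant. This holds the one-sided false-claim rate at 5% whatever the correlation (simulated 4.9–5.1%) and keeps single-test power. In choosing, the sponsor should consider which reading the independent observer takes, since Procedures has that observer assess "pain after the aromatherapy has been removed from the room". Keeping both times as co-primary, both required, is an acceptable alternative. It needs no alpha split, but power is 0.69–0.75 at SD 20.
3. State the role of 13 mm in the decision rule. The recommended role is a benchmark for interpreting the estimate and its confidence interval, not a condition on the observed difference.

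No extra patients or visits are needed, but two costs should be stated. First, the second time point can no longer carry a claim alone: its power in the ordered test is 0.69–0.75, against 0.80 on its own (true 13 mm at both times, SD 20). Second, relative to the literal reading at SD 20, dropping the 13 mm condition and the both-times requirement allows 5% false claims instead of at most 0.3%. Significance also becomes possible at observed differences below 13 mm, from about 8.6 mm. Whether to test one- or two-sided is a separate choice that this fix does not require.

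### Back pain and sciatica are pooled throughout: a sciatica yes/no factor and a descriptive result per condition would be a cheap improvement

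*Combined protocol and SAP*

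**What the plan says.** Section A names acute isolated back pain and sciatica as the study conditions, and the Rationale and Overview in Section D pairs them again: "Isolated acute back pain (less than 2 weeks duration) and sciatica are common complaints to the emergency department". Section B looks ahead to a finding that covers both: "Validity of Rosa damascene aromatherapy in acute back pain and sciatica may open new doors of pain control".

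Under Study Sample there is one sequence of vessels: "Randomization will then arrange the total 60 treatments in longitudinal order for sequential random treatments to be selected as each patient is recruited". Blocks are used, but no stratification factor is named. The sample size is 30 per arm, and its only stated basis is "based on a power of 0.80, desired p value below 0.05, and 95% confidence intervals". Section A sets the endpoint as "evaluation of significant change in VAS score greater than 13 mm between both groups".

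The Rationale and Overview also says "Pain will be qualified in its type, locations, duration", with other descriptors of the episode. Section E compares treatment with control as whole groups, by t-test and chi-squared test. It has no covariate, stratum or result by condition.

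**The concern.** Two named conditions enter one comparison, and nothing in the plan separates them. Two things follow.

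First, if VAS falls by a different amount in sciatica whichever oil is used, the spread between conditions stays in the error term. A chance difference in sciatica share between arms then shifts the observed contrast in that one trial.

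Second, a pooled result gives no information on sciatica itself. The pooled difference could exceed 13 mm with no effect in sciatica, and no planned output would show it. The protocol nevertheless hopes to learn about both conditions.

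**Working it through.** **Inputs from the documents.** 30 per arm, power 0.80, p below 0.05 (Study Sample); 13 mm (Section A); one-tailed testing (Section E). The SD of VAS change, the dropout rate, the sciatica share and the gap in mean VAS change between conditions are not given. The values used for these below are assumptions.

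**The plan's own figure.** 30 per arm cannot be reproduced without an SD. Solving backwards by the normal approximation with no dropout, SD = 13 / [√(2/30) × (z for alpha + z for power)]:
- two-sided: 13 / (0.2582 × 2.802) = 18.0 mm
- one-sided: 13 / (0.2582 × 2.486) = 20.2 mm

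An SD of 18 to 20 mm is therefore a reasonable working range.

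**Precision.** Let p be the sciatica share and d the gap between conditions. Residual SD after adjustment = √(SD² − p(1−p)d²). With SD 20 mm and p = 0.4 this is √(400 − 0.24d²). Noncentral-t power at 13 mm, 30 per arm, alpha 0.05:

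| Gap d (mm) | Residual SD (mm) | Two-sided power | One-sided power |
|---|---|---|---|
| no adjustment | 20.00 | 0.697 | 0.800 |
| 5 | 19.85 | 0.703 | 0.806 |
| 10 | 19.39 | 0.724 | 0.822 |
| 15 | 18.60 | 0.759 | 0.849 |

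Charging the extra degree of freedom changes these by about 0.001 at most.

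**Chance imbalance.** With K sciatica patients among 60 and 30 per arm, the number in one arm is hypergeometric (simple 30:30 allocation assumed, as no block size is given). The probability that the shares differ by at least 20 percentage points is 0.072 (K = 15), 0.170 (K = 20), 0.187 (K = 24) and 0.196 (K = 30). The shift in the contrast is imbalance × gap: 0.20 × 10 = 2 mm, or 0.20 × 15 = 3 mm. The standard error of the contrast at SD 20 mm is 20 × √(2/30) = 5.2 mm, so a 2 mm shift is about 0.4 standard errors.

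**A pooled effect carried by one condition.** Suppose rose oil gives 20 mm in isolated back pain, 0 mm in sciatica, and 30% have sciatica. The pooled difference is 0.7 × 20 + 0.3 × 0 = 14 mm, above 13 mm. Noncentral-t power for 14 mm is 0.84 two-sided and 0.91 one-sided at SD 18 mm, or 0.76 and 0.85 at SD 20 mm.

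**What a result within sciatica can show.** At SD 20 mm and a near-equal split between arms, the 95% half-width is t × 20 × √(1/n₁ + 1/n₂), with t on the patients in that condition:
- 15 patients (7 and 8): 2.16 × 10.35 = 22 mm
- 20 patients (10 and 10): 2.10 × 8.94 = 19 mm
- 24 patients (12 and 12): 2.07 × 8.16 = 17 mm

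An observed 13 mm in sciatica would still have an interval that includes zero.

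**The case against.** The strongest reply is that chance imbalance is not a fault in a randomised plan. It leaves the estimate unbiased on average and the type I error intact, and the unadjusted standard error already allows for it. That stands. The same could be said of any covariate left out of the allocation, and a shift of 2 to 3 mm is small beside a standard error of 5.2 mm.

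It also stands that the size is wholly assumed. Nothing in the documents says that VAS change over the hour differs by condition. At a 5 mm gap the power gain is under 0.01. It reaches 0.06 two-sided only at 15 mm, a gap wider than the 13 mm threshold.

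A pooled estimate is also a legitimate answer for a pooled population in a trial of 60. The sentence in Section B is conditional background, and Importance of the Knowledge to be Gained in Section G speaks only of acute back pain patients. A reader might infer that the plan commits itself to a separate efficacy claim for sciatica; it does not.

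None of this removes the narrower point. Sciatica is one of the conditions the trial sets out to learn about, and no planned output describes it.

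**Conclusion.** A cheap improvement, not an error in the plan. The structural facts are in the text: two conditions, one unstratified list and whole-group comparisons. The loss is modest and conditional. Between nothing and about 0.06 of two-sided power is forgone at a 40% share, SD 20 mm and gaps of 5 to 15 mm; one-sided, power goes from 0.80 to between 0.81 and 0.85. The more useful gain is a view of the effect in each condition, and the 14 mm illustration shows why that matters.

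Three further inferences are tempting and are not supported:
- **Different durations.** The two-week limit is worded next to isolated back pain only, so a reader might conclude that sciatica patients may have longer histories. The inclusion and exclusion criteria are attached to the protocol but are not in the supplied text, and they may settle this.
- **The factor already exists.** The protocol does not say that pain type is recorded before treatment, or that type separates sciatica from isolated back pain. Screening states that chief complaint is not recorded, so the item has to be defined.
- **A claim rule based on the sciatica interval.** With half-widths of about 17 to 22 mm, requiring that interval to support a claim would turn a descriptive result into a test the trial could not normally pass.

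**What to change.** 1. On the patient data sheet, define sciatica yes/no and complete it before the vessel is selected.
2. In Section E, include that item as a factor in the between-arm comparison of VAS change.
3. Report the rose-minus-almond difference with its 95% CI in each condition, labelled descriptive, with no test or decision attached.
4. Word the conclusion as applying to the pooled population of acute back pain and sciatica, not to sciatica separately.

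Two vessel lists of balanced blocks, one per condition and held by the same key-holder, are optional. The analysis factor alone gives the precision gain.

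Cost: one baseline item to define, one degree of freedom, and wide within-condition intervals that readers must be told not to over-read. If two lists are used, the number of vessels needed in each is not known in advance, and the overall split may depart slightly from 30/30. No extra patients, visits or change to treatment are needed.

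### The screening explanation calls aromatherapy proven for pain other than back pain, which is stronger than the protocol's own evidence account and an avoidable expectation cue for a self-rated endpoint

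*Combined protocol and SAP*

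**What the plan says.** Section D, Screening, sets out what the investigator tells each candidate: "Aromatherapy will be explained as the treatment of interest and a modality that has been tested and proven in other types of pain". Rose and almond products are then discussed briefly. The same section has the candidate told that taking part may bring no direct benefit. The text that follows lists the possibility that pain does not change among the risks explained before consent.

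On the state of the evidence, the protocol speaks in two registers.

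- Cautious: section A says "These studies have been small and specific to discrete clinical conditions" and that "they are not yet externally validated to more common conditions facing emergency medicine physicians". Section B opens with "Aromatherapy has been hypothesized to be an effective management strategy for acute pain control" and later adds "Its prior studies are small in sample size and carry little external validity".
- Favourable: section A describes rose oil as "shown to be effective versus placebos for the control of acute pain with lasting effects", citing burn-dressing and post-operative pain. Section B limits the finding against scented placebos to one oil: "only Rosa damascena has been shown to produce significant reduction in pain on the VAS".

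On blinding, section D, Procedures, concedes: "The patients will be aware that the study involves Rose and Almond scents and will likely be able to identify the scent used in their" [session]. The safeguard offered is an independent observer, unaware of allocation, who assesses pain at the end of the procedures once the scent has left the room. The primary endpoint (section A) is change on a 100 mm VAS at the end of the 30-minute treatment and again 30 minutes later. Section D, Rationale and Overview, makes clear that the patients place the marks on the line.

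**The concern.** The endpoint is the patient's own rating, and the patient can probably tell which oil is in use. In that setting, what patients are led to expect can move the measurement. A statement that the modality is already proven is a cue the trial does not need. It is given before consent, and so before the pre-treatment VAS.

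Two things are at stake. One is the rose-versus-almond contrast, which an expectation effect could shift or blur depending on how patients read the statement. The other is consistency: the description given to candidates should be no stronger than the one the protocol gives its own readers.

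**Working it through.** **Step 1: set the statements side by side.**

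| Point | Told to candidates (section D, Screening) | Protocol's own account |
|---|---|---|
| Strength of evidence | Tested and proven | Hypothesised; small studies; little external validity (sections A and B); but also shown effective against placebo in specific settings (section A) |
| What it applies to | Aromatherapy as a modality | VAS benefit over scented placebo credited to rose oil only (section B) |
| Which pain | Pain other than back pain | Burn dressings and post-operative pain; transfer to common emergency conditions not established (sections A and B) |

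The first row is a difference of degree, since the protocol has favourable statements as well as cautious ones. The second is a real widening: half the patients will inhale almond oil, the control, for which the protocol claims no benefit. The third row agrees.

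**Step 2: does the design absorb an expectation cue?** Not fully. The observer is unaware of allocation, but the patient makes the mark and will probably know the scent. The observer is described only at the end of the procedures, so the text does not place that person at the reading taken immediately after treatment.

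**Step 3: what could the cue do to the between-arm test?** Let b be the between-arm difference in expectation effect, in mm favouring rose, with no true effect of rose.

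Inputs:
- n = 30 per arm (section D, Study Sample).
- One-sided 5% level (section E specifies one-tailed tests; Study Sample gives 0.05). A two-sample comparison of VAS change between arms is assumed.
- SD of VAS change: not given, so assumed. For orientation, the SD at which 30 per arm gives 80% power for 13 mm, one-sided and with no dropout allowance, is 13 × √(30/2) / (1.645 + 0.842) ≈ 20.25 mm (20.01 mm by noncentral t). I use 20 mm, with 18, 25 and 30 mm as a range.
- b: not given, so assumed at 0, 3 and 5 mm.

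Formula: false-positive rate = 1 − Φ(1.645 − b / SE), with SE = SD × √(2/30).

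At SD 20, SE = 20 × 0.2582 = 5.164 mm.
- b = 0: 1 − Φ(1.645) = 0.050.
- b = 3: 3/5.164 = 0.581, so 1 − Φ(1.064) = 0.144 (0.142 by noncentral t, 58 df).
- b = 5: 5/5.164 = 0.968, so 1 − Φ(0.677) = 0.249 (0.246 by noncentral t).

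| Assumed SD (mm) | b = 0 | b = 3 mm | b = 5 mm |
|---|---|---|---|
| 18 | 0.050 | 0.159 | 0.285 |
| 20 | 0.050 | 0.144 | 0.249 |
| 25 | 0.050 | 0.119 | 0.192 |
| 30 | 0.050 | 0.104 | 0.159 |

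**Step 4: read the table.** The b = 0 column is equal priming of both arms: no inflation of false positives. What remains is a larger common placebo response, which may leave less pain for rose to reduce. That loss cannot be sized, because no baseline VAS is given. The other columns apply only if patients expect more from rose than from almond.

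**The case against.** The strongest reply is that the sentence is close to what the protocol says elsewhere. It is limited to other types of pain, section A reports benefit over placebo in such settings, and section B reports benefit in burn dressing and parity with NSAIDs after surgery. The main caveat in sections A and B concerns transfer to the emergency department, which the sentence does not assert. Candidates also hear that there may be no direct benefit and that pain may not change. This much stands: a reader might infer that the wording flatly contradicts the protocol, and the documents do not support that. The disclosures temper the message and are compatible with it.

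The second reply also stands. The sentence praises aromatherapy, both arms inhale a scent, and section G uses the term aromatherapy agent for whichever oil is assigned. Nowhere does the text say patients are told that rose is the active scent. A reader might infer that the wording must distort the contrast in favour of rose, or that the 14% and 25% rates measure its effect. Neither follows. Those rates need an assumed between-arm difference in expectation, and such a difference could arise from scent recognition whatever the wording.

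Two further inferences go too far. That the wording selects believers is not shown, and such selection would precede randomisation, so it would bear on generalisability and not on balance between arms. That patients consent on an overstated benefit cannot be judged either, because the consent form is not available to this review.

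What the replies do not remove is that *proven* outruns *hypothesized* and *small*, and that a result credited to rose is stated for aromatherapy in general.

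**Conclusion.** The point holds as a matter of wording and avoidable risk. The screening explanation is stronger and broader than the protocol's evidence account, and it reaches patients before they rate their own pain under blinding that the protocol admits is incomplete.

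The consequence is conditional. Equal priming leaves the false-positive rate at 5% and may blunt sensitivity. Differential priming towards rose would inflate it, to roughly 10% to 16% for 3 mm and 16% to 29% for 5 mm across assumed SDs of 30 down to 18 mm. The SDs and shifts are assumptions. I am confident about the mismatch in wording; any bias in the contrast is possible but not demonstrated.

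**What to change.** Replace the sentence under Screening with neutral wording that treats the two scents alike, for example: *We are comparing two scents, rose and almond; it is not known whether either one reduces back pain.* Delete the claim that the modality is tested and proven, and use the same neutral wording in the consent discussion. Keep the existing statements that there may be no benefit and no change in pain.

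The cost is one sentence in the protocol and the matching wording in the consent discussion, with no extra patients, staff or procedures. Willingness to enrol may fall slightly. Patients will still probably recognise their scent, so incomplete patient blinding needs its own answer.
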